#### Study design

This is a Phase I randomised, double-blind, placebo-controlled, parallel group study in a single study centre to assess the safety, tolerability, and pharmacokinetics of ceftaroline fosamil administered in healthy subjects.

Approximately 40 healthy male and female subjects will be enrolled in 2 cohorts (Cohort 1 and Cohort 2) 20 subjects per cohort with 15 receiving ceftaroline and 5 receiving placebo. Cohort 1 will receive a single intravenous infusion on Day 1 and Day 8 with 2 daily infusions (12 hourly) on Days 2-7, infused over 1 hour. Cohort 2 will receive single intravenous infusion on Day 1 and Day 8 with 3 daily infusions (8 hourly) on Days 2-7 hours, infused over 2 hours.

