#### Investigational product, dosage and mode of administration

Multiple intravenous infusions of ceftaroline fosamil starting with a single infusion of 600 mg on Day 1 followed by multiple daily infusions Days 2 to 7, with a single 600 mg infusion on the morning of Day 8.

Cohort 1 will receive a single intravenous infusion on Day 1 and Day 8 with 2 daily infusions (12 hourly) on Days 2-7, infused over 1 hour.

Cohort 2 will receive single intravenous infusion on Day 1 and Day 8 with 3 daily infusions (8 hourly) on Days 2-7 hours, infused over 2 hours.

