## 3.1 Overall study design and flow chart

This is a Phase I, randomised, double-blind, placebo-controlled, parallel group study in healthy male and female subjects conducted at a single study centre. Up to 40 healthy subjects aged 18 to 55 years (inclusive) will participate in 2 cohorts. Each cohort will be divided into 4 subgroups of 5 subjects each.

Twenty subjects will participate in each cohort and will receive either ceftaroline fosamil (15 subjects) or placebo (5 subjects). Each subject will only participate in 1 cohort. The dose will be 600 mg 12-hourly (infused over 1 hour) in Cohort 1 and 600 mg 8-hourly (infused over 2 hours) in Cohort 2.

[figure not shown]
After a screening period of up to 28 days, subjects will be admitted to the study centre on Day -1, discharged on Day 9 and followed up 7 to 10 days after discharge (see Figure 1).

On Days 1 and 8 subjects will receive a single dose of 600 mg ceftaroline fosamil or placebo.

Repeated infusions will commence on Day 2. Subjects will then receive ceftaroline fosamil or placebo every 12 hours (Cohort 1) or every 8 hours (Cohort 2) from Days 2 to 7. It is anticipated that this will be sufficient to achieve and maintain steady state for several days and evaluate the safety of multiple infusions adequate for the intended target. Throughout the residential period there will be safety monitoring and serial blood samples for PK evaluation (for details see Figure 3).

Local tolerability will be assessed according to the VIP scale. The VIP score will be recorded for all local reactions; any local reaction with a VIP score of 2 or greater will be determined as an ISR and will be recorded as an adverse event. See Section 6.3.1.

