#### 5.2.1 **Procedures for randomisation**

A randomisation scheme will be produced by using the AstraZeneca global randomisation system (GRand). Subjects will be allocated to ceftaroline fosamil or placebo (15 subjects to ceftaroline fosamil and 5 subjects to placebo per cohort). The randomisation will be done for each cohort using consecutive randomisation codes (subject numbers).

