# **11.2** Methods of statistical analyses

## **11.2.1** General principles

Data will be presented by actual dose (not by cohort), and subjects receiving placebo will be pooled across dosing cohorts for the purposes of summarising the safety results.

Given the exploratory nature, no formal statistical hypothesis testing will be performed in this study. Since no planned formal testing will be performed in this study, and the confidence intervals that will be calculated are only for descriptive purposes, no corrections for multiplicity will be used.

Missing data will result in a reduced sample size for that parameter. Since the statistical analyses will be predominantly presentations in tables and individual data listings, no action will be taken to handle missing data.

A subject who withdraws prior to the last planned observation in a study period will be included in the analyses up to the time of discontinuation.

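### Placebo is pooled across two different infusion schedules even for local tolerability, so the planned summaries do not show each regimen beside its own same-schedule placebo group

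*Protocol*

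**What the plan says.** Section 11.2.1 sets the rule for every safety summary: "subjects receiving placebo will be pooled across dosing cohorts for the purposes of summarising the safety results". Section 11.2.3 then summarises safety and tolerability by treatment group and defines no placebo group per cohort.

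The two schedules differ. Under Study design in the synopsis, both cohorts have one infusion on Day 1 and one on Day 8. Between those days Cohort 1 is treated "with 2 daily infusions (12 hourly) on Days 2-7, infused over 1 hour" and Cohort 2 "with 3 daily infusions (8 hourly) on Days 2-7 hours, infused over 2 hours" (the word after the day range is evidently a slip). Section 3.1 confirms that placebo subjects follow their cohort's timetable: "Subjects will then receive ceftaroline fosamil or placebo every 12 hours (Cohort 1) or every 8 hours (Cohort 2) from Days 2 to 7".

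Section 5.2.1 allocates 15 subjects to active and 5 to placebo in each cohort, and adds: "The randomisation will be done for each cohort using consecutive randomisation codes". The primary objective (Section 2.1) is the safety and tolerability of the different regimens relative to placebo. Section 3.2 gives the purpose of placebo as telling drug effects apart from effects of the study procedures. Appendix E accepts that an infusion-site reaction can come from the cannula or from infusing placebo. Section 6.3.1 makes a VIP score of 2 or more an adverse event.

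**The concern.** Pooling placebo over Phase I cohorts is a sound convention when placebo subjects go through the same procedures. Here the procedure, intravenous infusion, is what differs between cohorts, and for local tolerability it is also a possible cause of the event being counted. The contrast protected by randomisation is each active arm against the placebo group of its own cohort. The pooled column replaces it with a mixture of two schedules.

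Sections 1.2 and 1.3 show that this bears on the study's purpose. The study is meant to characterise the safety of longer infusions and to evaluate the two regimens properly on safety and tolerability. Injection-site pain and thrombophlebitis are named among the main risks. Because VIP scores of 2 or more become adverse events, any mismatch reaches the adverse event tables as well as the VIP summaries.

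**Working it through.** **The plan's own figures.** Total subjects: 2 × (15 + 5) = 40, as stated. Daily doses: 2 × 600 = 1200 mg and 3 × 600 = 1800 mg, as in Section 5.5.2. The schedules are therefore read as intended.

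**Placebo exposure by cohort.** Infusions = 1 (Day 1) + k × 6 (Days 2 to 7) + 1 (Day 8).
- Cohort 1, k = 2: 1 + 12 + 1 = 14 infusions × 1 h = 14 h.
- Cohort 2, k = 3: 1 + 18 + 1 = 20 infusions × 2 h = 40 h.
- Ratio, Cohort 2 to Cohort 1: 20/14 = 1.43 for infusions and 40/14 = 2.86 for hours.
- Pooled placebo, 5 + 5 subjects: (14 + 20)/2 = 17 infusions and (14 + 40)/2 = 27 h.

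**Possible distortion.** The protocol gives no infusion-site reaction rate, so every p below is an assumption. Suppose the drug has no effect on these reactions. The risk of at least one reaction is 1 − (1 − p)^m, where m is the number of infusions or of infusion-hours. With 5 placebo subjects per cohort, the pooled risk is the mean of the two. The shift is the distance from each cohort's true background to that mean.

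| Assumed risk | Cohort 1 | Cohort 2 | Pooled | Shift (points) |
|---|---|---|---|---|
| Follows cannula days (taken as equal in both cohorts) | same | same | same | about 0 |
| 0.5% per infusion | 6.8% | 9.5% | 8.2% | ±1.4 |
| 2% per infusion | 24.6% | 33.2% | 28.9% | ±4.3 |
| 5% per infusion | 51.2% | 64.2% | 57.7% | ±6.5 |
| 0.5% per hour | 6.8% | 18.2% | 12.5% | ±5.7 |
| 1% per hour | 13.1% | 33.1% | 23.1% | ±10.0 |
| 2% per hour | 24.6% | 55.4% | 40.0% | ±15.4 |

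Where the shift is not zero, its sign is fixed. The pooled column overstates the background for Cohort 1 and understates it for Cohort 2.

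**Precision given up by splitting.** The exact two-sided 95% upper limit for 0 events in n subjects is 1 − 0.025^(1/n): 52.2% for n = 5 and 30.8% for n = 10.

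**Accuracy of each estimate of a cohort's own background.** Mean squared error is bias squared plus binomial variance.
- 1% per hour, Cohort 1: separate 0.131 × 0.869/5 = 0.023; pooled 0.100² + 5 × (0.131 × 0.869 + 0.331 × 0.669)/100 = 0.027.
- 1% per hour, Cohort 2: separate 0.331 × 0.669/5 = 0.044; pooled 0.027.
- 2% per infusion, Cohort 1: separate 0.246 × 0.754/5 = 0.037; pooled 0.043² + 5 × (0.246 × 0.754 + 0.332 × 0.668)/100 = 0.022.
- 2% per infusion, Cohort 2: separate 0.332 × 0.668/5 = 0.044; pooled 0.022.

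Pooling is the more accurate in three of these four cases.

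**The case against.** The strongest reply is about precision. One event among 5 subjects moves a column by 20 points, which is more than any shift in the table, and the mean squared errors usually favour the pooled estimate. That stands. It rules out replacing the pooled column, but not showing the cohort columns beside it.

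The risk model is also open. Appendix E names cannula insertion, patency and maintenance as causes, and both cohorts are resident and dosed over the same days. If placebo risk follows cannula time, pooling does no harm. That stands too, so the size of the shift cannot be asserted.

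Nothing is formally tested, the stopping rule in Section 5.8.1 counts related serious adverse events only, and individual listings are planned. This limits the consequences. Even so, descriptive tables are the study's main evidence on its primary objective, so the choice of comparator column still matters.

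Two stronger readings are tempting and are not supported:
- A reader might infer that the design lacks a like-for-like control. It does not: each cohort randomises 5 placebo subjects to its own schedule, and only the summaries leave them undisplayed.
- A reader might infer unequal detection, with 3 × 14 = 42 against 3 × 20 = 60 VIP readings. Figure 2 marks local tolerability by day, and its footnote gives three times around dosing without saying that every infusion is covered. Read as once daily over Days 1 to 8, both cohorts have 3 × 8 = 24.

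**Conclusion.** The point holds as one of presentation, limited to local tolerability. The pooling rule has no exception, the two placebo groups differ 1.43-fold in infusions and 2.86-fold in infusion time, and the planned summaries omit the same-schedule contrast that randomisation provides.

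The exposure figures follow directly from the protocol. The distortion does not. It ranges from about 0 if risk follows cannula days, through about 4 points at 2% per infusion, to 6 to 15 points at 0.5% to 2% per infusion-hour. Its direction, against the 8-hourly regimen and in favour of the 12-hourly one, is conditional on risk rising with the number or hours of infusions. The argument does not extend to systemic adverse events, laboratory values, ECG or vital signs, where the pooled 10 subjects remain the better comparator. This is a minor, cheap improvement.

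**What to change.** Add an exception to Section 11.2.1: for VIP scores and infusion-site adverse events, placebo is shown by cohort (n = 5 each) beside the active arm of the same cohort, in addition to the pooled placebo column (n = 10). All other safety summaries keep pooled placebo alone.

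The cost is two extra columns in a few tables, with no new data and no change to design or randomisation. A footnote should warn that each cohort column rests on 5 subjects, so that a zero count is not read as absence of risk.

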#### **Outcome variable(s):**

• Safety (primary)

Adverse events, laboratory variables, vital signs, electrocardiogram, and physical examination

• Pharmacokinetics

Where possible, the following plasma and urine pharmacokinetic parameters will be determined for ceftaroline fosamil (the prodrug of ceftaroline), ceftaroline, and ceftaroline M-1, unless otherwise noted. Other pharmacokinetic parameters may also be calculated if deemed appropriate.

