The safety data revealed that potential adverse cardiac, renal, or hepatic effects with the administration of ceftaroline fosamil were similar to those observed for other cephalosporins. The risk of allergic reactions to ceftaroline appears to be similar to that of the comparators studied, and although 2 seizures were observed in subjects who received ceftaroline fosamil, both occurred more than 2 days after completion of ceftaroline fosamil therapy. Cephalosporins are known to be associated with positive direct Coombs' test results. Although rates of sero-conversion from a negative to a positive direct Coombs' test were higher in the ceftaroline group compared with the comparator groups, no subject was identified with clinical findings or laboratory results that were consistent with haemolytic anaemia. The incidence of potential antibiotic-associated diarrhoea (which can occur with most antibiotics) was low and similar in subjects who received ceftaroline fosamil compared with comparator therapies and resulted in similar numbers of subjects prematurely discontinued from investigational product administration or from the study due to TEAEs of diarrhoea in both treatment groups. Confirmed cases of *Clostridium difficile*-associated diarrhoea were rare in both treatment groups.

At the clinical dose levels of ceftaroline fosamil studied (600 mg intravenously every 12 hours or 400 mg intravenously every 12 hours); ceftaroline demonstrated an acceptable safety profile that was compatible with treatment of cSSSIs and CABP. In addition, no safety concerns were identified in the safety review beyond those already known to be cephalosporin class effects.

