#### 5.3 **Procedures for handling incorrectly randomised subjects**

**Subjects who fail to meet the inclusion/exclusion criteria** should not, under any circumstances, be enrolled or receive the investigational product. There can be no exceptions to this rule.

Where a subject, who does not meet the inclusion and/or exclusion criteria, is randomised in error and this is identified before the investigational product administration, the subject should be withdrawn from the study. A discussion should occur between the AstraZeneca CPA Physician and the Investigator regarding whether a replacement may be considered.

Where a subject, who does not meet the selection criteria, is randomised in error and started on treatment, or where a subject subsequently fails to meet the study criteria post-initiation, the Investigator should inform the AstraZeneca CPA Physician immediately. Although treatment should be discontinued, the subject should be advised to continue assessments to ensure their safety.

The AstraZeneca CPA Physician is to ensure all decisions are appropriately documented.

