# 5.8 Discontinuation of investigational product and withdrawal from study

Subjects may be discontinued from investigational product in the following situations:

- Subject decision. The subject is at any time free to withdraw his/her participation in the study, without prejudice
- AEs
- Severe non-compliance to the CSP, as judged by the Investigator and/or AstraZeneca
- Randomisation in error (see Section 5.3)

Investigational product administration for any individual subject will be stopped if the subject experiences a possible drug-related SAE or a possible drug-related significant non-serious AE, which in the opinion of the Investigator or Sponsor, warrants discontinuation from the study for that subject's well-being.

Subjects who discontinue investigational product administration will be withdrawn from the study.

Subjects who are withdrawn from the study by the Investigator due to AEs after the start of the investigational product administration will not be replaced. Subjects who withdraw for any reason before the first investigational product administration or for reasons other than AEs after the start of the investigational product administration may be replaced.

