#### 5.8.2 Procedures for withdrawal of a subject from the study

Subjects are at any time free to withdraw from the study (study treatment and assessments), without prejudice (withdrawal of consent). Such subjects will always be asked about the reason(s) and the presence of any AEs. If possible, subjects who withdraw from the study after the start of investigational product administration and before completion should be seen by an Investigator and undergo the assessments and procedures scheduled for the follow-up visit. Adverse events should be followed up (see Sections 6.3.4 and 6.3.5).

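### Section 11.2.1 cuts a withdrawn subject's data at discontinuation without exempting safety, although the protocol plans safety data after that point

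*Protocol*

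**What the plan says.** The synopsis names safety as the primary outcome: adverse events, laboratory variables, vital signs, ECG and physical examination.

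Section 11.2.1 sets a general rule for a subject who leaves before the last planned observation. Such a subject "will be included in the analyses up to the time of discontinuation". The rule speaks of the analyses as a whole and is not restricted to pharmacokinetics.

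Section 5.8 ties stopping treatment to leaving the study: "Subjects who discontinue investigational product administration will be withdrawn from the study".

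Other sections plan safety data after that point:
- Section 5.8.2 asks that subjects who withdraw after dosing has begun should, if possible, be seen and "undergo the assessments and procedures scheduled for the follow-up visit". It also asks for follow-up of adverse events.
- Section 5.3 says of subjects randomised in error and already treated: "Although treatment should be discontinued, the subject should be advised to continue assessments to ensure their safety".
- Section 6.3.4 collects adverse events from randomisation through the follow-up period.
- Section 11.2.3 describes collection until the follow-up visit, separates only pre-dose events, and then summarises adverse events by preferred term and system organ class. It has no cut-off at discontinuation.

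**The concern.** A cut-off at discontinuation is natural for pharmacokinetic data, because concentrations after dosing stops no longer describe the regimen. It is a poor rule for safety. A reaction or laboratory change can first appear after the last infusion, and a subject who stopped early may have stopped because of treatment. Section 5.8 adds that subjects withdrawn for adverse events are not replaced, and 11.2.1 says that nothing will be done about missing data, so nothing offsets the loss.

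Appendix D gives an example from the protocol itself. Potential Hy's law may be met by transaminase and bilirubin values from different visits, with no time limit between them. A value obtained after discontinuation could complete the criterion and yet, on the literal rule, be absent from the laboratory summaries. Investigator reporting under Appendix D would not be affected.

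At stake is whether the primary safety tables contain all the safety data that the protocol collects. With arms this small, one event is visible in the result.

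**Working it through.** **Which data the rule reaches**

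| Step | Source | Content |
|---|---|---|
| 1 | 5.8 | Stopping product leads to study withdrawal |
| 2 | 11.2.1 | A withdrawn subject is analysed up to discontinuation; no safety exemption |
| 3 | 5.8.2 | Follow-up visit assessments after withdrawal, if possible; adverse events followed up |
| 4 | 6.3.4, 11.2.3 | Adverse events collected through the follow-up period or visit |
| 5 | 11.1.2 | Defines which subjects enter the safety set, not which time window of their data |
| 6 | 11.2.3 | Separates only pre-dose events; neither repeats nor lifts the cut-off |

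Steps 1 and 2 together apply the cut-off to everyone who stops infusions early. Steps 3 and 4 show that data are planned beyond it. Steps 5 and 6 contain nothing that brings those data back in. The literal rule therefore excludes data that are collected.

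**Size of one excluded event**

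Inputs:
- Allocation per cohort is 15 active and 5 placebo (5.2.1).
- Placebo is pooled across cohorts for safety (11.2.1), so 5 + 5 = 10.
- The plan wants 12 of 15 active subjects to complete each cohort (synopsis, target population), which allows for 15 − 12 = 3 non-completers, or 3/15 = 20%.

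Effect of one event on an incidence:
- Active arm: 1/15 = 6.7 percentage points.
- Pooled placebo: 1/10 = 10 points.
- If the two active regimens were pooled: 1/30 = 3.3 points.

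For illustration, assume that no other subject has the event and that each affected non-completer has it for the first time after discontinuation. Under the cut-off the active arm shows 0/15, with an exact (Clopper-Pearson) 95% interval of 0 to 21.8%. With those events counted:

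| Affected subjects | Incidence | Exact 95% interval |
|---|---|---|
| 1 | 1/15 = 6.7% | 0.2 to 31.9% |
| 2 | 2/15 = 13.3% | 1.7 to 40.5% |
| 3 | 3/15 = 20.0% | 4.3 to 48.1% |

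In pooled placebo one such event moves 0/10 (0 to 30.8%) to 1/10 = 10% (0.3 to 44.5%).

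The protocol gives no figure for this effect, so there is none to reproduce. The sample size is stated to have no formal basis and does not change.

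**The case against.** The strongest reply is that the sentence in 11.2.1 is an inclusion rule. It follows the paragraph on missing data and may only mean that partial data from withdrawn subjects are kept and nothing is imputed. Discontinuation could also mean the end of participation, in which case the withdrawal assessments of 5.8.2 fall inside the window. Section 11.2.3, the more specific text, has no cut-off and covers collection up to follow-up. Much of this stands. The protocol does not say that data are used only up to discontinuation, and nowhere does it expressly order collected safety data to be discarded. But 11.2.3 does not lift the general rule, so two readings remain and they can give different primary safety tables.

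Several stronger inferences are tempting but not supported:
- **Events that cause withdrawal are lost.** They are not. They start before the cut-off, and 11.2.3 lists and counts them. The study stopping rule in 5.8.1 works on reported serious events and is unaffected.
- **The two past seizures show what would be missed.** Section 1.1 says that "both occurred more than 2 days after completion of ceftaroline fosamil therapy". They followed completed treatment, and completers are not withdrawn subjects. In an early discontinuer, a convulsion would normally be reportable as serious under Appendix B.
- **A fixed off-drug window is lost.** Section 5.8.2 sets no date for the assessments of a withdrawn subject and asks for them only if possible, so no number of days can be stated.
- **Sections 5.3 and 5.8 flatly contradict each other.** Section 5.8.2 provides for assessments after withdrawal and largely resolves this. The wording still needs aligning.

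It is also fair that the study is descriptive, that the rule applies to placebo as well, and that safety windows are often set in the analysis plan. The last point does not dispose of the matter, because the protocol has already stated a rule that an analysis plan must either follow or depart from.

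**Conclusion.** The concern holds as a wording defect in 11.2.1 that should be corrected. Read literally, the sentence leaves safety events and values first seen after discontinuation out of the primary safety summaries, and it is out of line with 11.2.3.

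The size is 6.7 points per event in an active arm of 15 and 10 points in pooled placebo. If all 3 non-completers allowed for in an active arm were affected, the difference would reach 20 points. That upper figure assumes the literal reading, separate reporting of the two active regimens, and one late first event in each non-completer. It illustrates the sensitivity of the tables and does not forecast what will happen. In practice few subjects are likely to be involved. The documents do not establish that the sponsor intends to drop these data, nor how large any bias would be.

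**What to change.** Amend 11.2.1 to state that all safety data collected through the follow-up visit (adverse events, laboratory, ECG, vital signs, physical examination and local tolerability) are included in the safety analyses for every subject in the safety analysis set, regardless of when infusions stopped. Limit the sentence on inclusion up to discontinuation to pharmacokinetic data. Reconcile the wording of 5.3, 5.8 and 5.8.2 so that they describe assessments after stopping in the same terms.

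The cost is a protocol wording change, carried into the analysis plan. The assessments are already planned, so no visit, sample, subject or test is added.
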